9.6 Abramson Cancer Center Data Safety Monitoring Committee (DSMC):

Every effort should be made to report an event as a diagnosis, not as a list of symptoms. Symptoms that led to the diagnosis should be included in the event description but should not be the actual event.

Unless covered by exclusions below, Grade 3 or higher events must be reported within 10 days of knowledge.

All unexpected deaths within one business day of knowledge.

All other deaths within 30 days of knowledge. Deaths of subjects off-study for greater than 30 days from the last study treatment/intervention are not reportable unless a longer time frame is specified in the protocol.

EXCEPTIONS to AE/SAE Reporting:

Grade 3 or 4 events that are judged by a study investigator to be clearly unrelated to protocol therapy. The reason for determining that the event is unrelated must be clearly documented in the EMR.

Grade 3 or 4 events that are probably or definitely related to progression of disease as judged by a study investigator. The fact that this event is related to disease progression must be clearly document in the EMR.

Grade 3 or 4 events that are probably or definitely related to an FDA approved agent. The fact that this event is related to the FDA approved agent must be clearly documented in the EMR..

SAEs will be submitted to the DSMC through the Velos Clinical Trial Management System.

Reportable Events;

Exception

CONFIDENTIAL

A one-time, intentional action (planned prospectively) or process that departs from the IRB and CTSRMC approved study protocol, intended for one occurrence. Advance documented IRB and DSMC approval is required.

For in-house studies with a Medical Monitor or Safety Monitoring Committee (not DSMB), approval must be obtained from the Medical Monitor or Safety Monitoring Committee prior to submitting your exception request to the DSMC.

The following information must be contained in your exception request:

- When it is needed and why it is needed in that timeframe
- Has the Medical Monitor or Sponsor approved and provide the documentation of approval
- Is this an exception from eligibility, treatment, disease progression, study calendar windows, etc.
- Why the exception is needed (cite the section(s) of the protocol) along with the full clinical details of the subject. This must be determined by the sub-Investigator or PI.

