- The reason why the protocol currently doesn't allow the situation for which an exception is being requested. This must be determined by the sub-Investigator or PI.
- If there are plans to amend the protocol and if not, why not.
- If additional follow-up or interventions will be required in order to protect the subject as a result of this exception.

Study Exceptions the DSMC may Reject:

Exceptions to eligibility, treatment/dosing, contraindicated treatment/therapies/interventions or safety tests for the following types of studies may be rejected by the DSMC:

- Any investigator-initiated treatment study.
- Any treatment study involving on-campus manufacturing of any component, regardless of sponsor.

To seek approval, you must provide the DSMC with strong and compelling scientific and clinical information to support your request. You should also include a statement explaining whether or not the protocol will be amended. If the protocol will not be amended your reasoning must be provided. If this situation is likely to happen again, the DSMC will require a protocol amendment.

Deviation

Any unintentional action or process that departs from IRB approval and is identified retrospectively. The deviation is reportable to the DSMC and the IRB within 10 days from the time the event becomes known to the study team only when: one or more participants were placed at increased risk of harm, or, the event has the potential to occur again, or the event has the potential to qualify as serious or continuing noncompliance.

If the PI determines that a deviation has **any potential** to impact participant safety (harm and/or risk), or the integrity of data produced from the participant, or some other overall impact on the study, the PI must report the deviation to the IRB and DSMC as described above. The IRB will make the final assessment of the impact. The DSMC will assess for additional safety and scientific integrity concerns.

The following information must be contained in your deviation report:

- When it happened? When the study team (any member) became aware
- The full description of the deviation including important dates, test results, actions taken towards the subject, etc. Also, why it happened and how it was identified.
- Was the Medical Monitor or Sponsor notified. If so, their response?
- The PIs assessment of the impact on risk, safety and/or outcome. If no impact, why. If impact, what and what will happen next.

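### The FDA-approved-agent exception in section 9.6 does not exclude the study drugs, so read literally it exempts Grade 3–4 events firmly attributed to them from 10-day DSMC reporting

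*Combined protocol and SAP*

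**What the plan says.** Section 9.6 sets the default for DSMC reporting: "Unless covered by exclusions below, Grade 3 or higher events must be reported within 10 days of knowledge". Three exceptions follow, under a heading that covers both AE and SAE reporting:

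- "Grade 3 or 4 events that are judged by a study investigator to be clearly unrelated to protocol therapy"
- "Grade 3 or 4 events that are probably or definitely related to progression of disease as judged by a study investigator"
- "Grade 3 or 4 events that are probably or definitely related to an FDA approved agent"

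The only condition on the third is documentation: "The fact that this event is related to the FDA approved agent must be clearly documented in the EMR". No section defines an FDA approved agent for this purpose or says whether the study drugs count as such.

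After the exceptions comes one unqualified sentence on serious events: "SAEs will be submitted to the DSMC through the Velos Clinical Trial Management System".

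Deaths have their own timelines in 9.6: one business day if unexpected, otherwise 30 days. The limit is "Deaths of subjects off-study for greater than 30 days from the last study treatment/intervention are not reportable", unless the protocol sets a longer period.

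Section 9.4 gives the causality scale, rated against study therapy: definitely, probably, possibly, unlikely or unrelated.

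**The concern.** An expedited safety rule would normally bring in the events most firmly attributed to study treatment. Here the wording can do the reverse: firmer attribution to an approved study drug removes the 10-day report, and weaker attribution keeps it. Two investigators could also apply 9.6 in opposite ways to the same event and both be following the text.

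This matters because the combination's tolerability in hepatocellular carcinoma is an assumption. Sections 1.1 and 1.4 carry it over from abemaciclib with pembrolizumab: ongoing breast and lung cancer studies, and a phase 1b breast cancer study that used 150 mg twice daily, this trial's starting dose. That is a reasoned bridge, but no safety data on abemaciclib with nivolumab are cited. Grade 3–4 events attributed with confidence to treatment are the ones that would test the assumption.

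**Working it through.** The plan gives no figure to reproduce, so the check sets the relevant sections side by side.

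**Step 1. Do the study drugs fit the wording?** Section 1.3 calls nivolumab FDA approved and lists hepatocellular carcinoma among its indications; section 1.3.1 describes the accelerated approval in this disease. Section 1.2.1.1 refers to an approved recommended abemaciclib dosage of 150 mg, and section 1.2.1.2 refers to its FDA package insert. Both drugs fit.

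**Step 2. Apply 9.6 to each level of the 9.4 scale.** Take a Grade 3–4 event for which neither progression nor a non-study approved agent is the probable or definite cause. Treat a rating against study therapy as a rating against its approved components; that is an inference, because 9.4 rates study therapy as a whole.

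| Relation to study drug | 9.6 read literally | Exception limited to non-study agents |
|---|---|---|
| Definitely | Exempt, note in record | Due in 10 days |
| Probably | Exempt, note in record | Due in 10 days |
| Possibly | Due in 10 days | Due in 10 days |
| Unlikely | Due, unless judged clearly unrelated | Same |
| Unrelated | Exempt if clearly unrelated | Same |

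Only the two strongest attributions change between the readings. The table shows the direction of the effect and not its size, since the levels will not hold equal numbers of events.

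**Step 3. Serious and non-serious events.** The Velos sentence can be read in two ways. If it is a free-standing duty, all serious events reach the DSMC and the literal exemption affects only non-serious Grade 3–4 events. If it only names the submission system, serious Grade 3–4 events are exempt too. Its lack of any qualifier favours the first reading; its place after exceptions that expressly cover SAE reporting favours the second. The non-serious events are affected either way.

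**Step 4. What other routes catch.**

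- Manufacturer (9.5.2): all SAEs and adverse events of special interest, within 1 business day.
- IRB (9.5.3): events both unexpected and related, within 10 working days. Side effects more severe or frequent than expected are also reportable (9.5.5), with no stated deadline.
- Medical monitor (11.1): serious events, at least every 6 months, with consultation on stopping.
- Internal audit (11.1): twice yearly, by the Cancer Center's Data Safety Committee.
- Recording and tabulation of all adverse events (9.3, 7.10.6, 8.4.3).

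None of these, as described, is prompt DSMC reporting. An expected, non-serious Grade 3–4 event clearly due to a study drug could miss both the 10-day DSMC route and the 10-working-day IRB route.

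**Step 5. Can the number of events be estimated?** No. The documents give no share of events by attribution. The abemaciclib toxicity rates in section 1.2.1.2 come from 200 mg twice daily in one study and from use with fulvestrant in the other.

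**The case against.** The best reply is that the exception was never meant to reach the study drugs. The first exception speaks of protocol therapy, so a different term in the third may mean something else. All three can be read as causes other than study treatment. Section 1.2 and the study summary label abemaciclib the investigational product. This reading is plausible, but it is not written, and the investigational-product label does nothing for nivolumab, the drug the protocol records as approved in this disease.

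A second reply is that leaving known toxicity of approved drugs out of expedited reports is a recognisable choice. The IRB rule also omits related events that are expected, and judges expectedness partly from product labelling. That stands, and the IRB rule should not be cited as a contradiction of 9.6. But the 9.6 exception is not limited to labelled or expected events, so it reaches further than that rationale.

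A third reply is that the answer may lie elsewhere. Section 11.1 calls for a site data and safety-monitoring plan and a study-specific data review plan, neither of which is in these documents. Parts of 9.6 read as committee-wide text, for example the reference to "Any treatment study involving on-campus manufacturing of any component, regardless of sponsor", and the investigators may not be free to edit it. This affects where the fix goes, not whether the protocol as it stands is ambiguous.

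A reader might infer that the DSMC would never learn of study-drug toxicity, or that the trial lacks safety oversight. The documents do not support either: deaths remain reportable within the stated limits, the other routes remain, and the body that conducts the twice-yearly audit appears to be the DSMC or closely related to it, although the names differ slightly.

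**Conclusion.** The point holds as a gap in the reporting rule with a limited effect. As written, 9.6 allows Grade 3–4 events firmly attributed to abemaciclib or nivolumab to skip 10-day DSMC reporting while less firmly attributed ones do not, and nothing in the documents rules that reading out. On that reading, what changes is what the DSMC sees and when: certainly for non-serious Grade 3–4 events, and for serious ones only if the Velos sentence is no more than a submission route.

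The size is qualitative. It would be tempting to count the levels of the causality scale as a magnitude, but a count of labels says nothing about how many events or subjects are affected.

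The conclusion rests on three assumptions: that the exception is applied as worded, that a rating against study therapy carries over to its component drugs, and that no monitoring plan outside these documents settles the question. No decision rule in the protocol depends on the 10-day reports, so neither the efficacy analysis nor the final safety tables are affected. This is a cheap improvement worth making, not a flaw that undermines the trial.

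**What to change.** Limit the third exception in 9.6 to Grade 3 or 4 events probably or definitely related to *an FDA approved agent other than the protocol therapy (abemaciclib, nivolumab or their combination)*. Add one sentence saying whether all SAEs go to the DSMC through Velos regardless of the exceptions, or whether Velos is only the submission route. If 9.6 is institutional text that cannot be edited, put both statements in as a study-specific reporting requirement.

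If the narrow reading was always intended, this only confirms it. If the literal reading was intended, the protocol should say so openly and explain why.

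The drafting cost is about two sentences. The running cost is more expedited reports, many on expected toxicity. No new data are needed, because these events are already recorded for the safety analysis.

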10.1 Confidentiality

Information about study subjects will be kept confidential and managed according to the requirements of the Health Insurance Portability and Accountability Act of 1996 (HIPAA). Those regulations require a signed subject authorization informing the subject of the following:

- What protected health information (PHI) will be collected from subjects in this study
- Who will have access to that information and why
- Who will use or disclose that information
- The rights of a research subject to revoke their authorization for use of their PHI

In the event that a subject revokes authorization to collect or use PHI, the investigator, by regulation, retains the ability to use all information collected prior to the revocation of subject authorization. For subjects that have revoked authorization to collect or use PHI, attempts should be made to obtain permission to collect at least vital status (i.e. that the subject is alive) at the end of their scheduled study period

10.2 Data Collection and Management

This study will use Velos as the data management system. The study case report form (CRF) is the primary data collection instrument for the study and will be electronically created and completed in Velos. CRFs will be provided for each subject. Subjects must not be identified by name on any CRFs. Subjects will be identified by their subject identification number (PID). All data requested on the CRF must be recorded. All missing data must be explained. If a space on the CRF is left blank because the procedure was not done, or the question was not asked, write "N/D". If the item is not applicable to the individual case, write "N/A." All entries should be printed legibly in black ink. If any entry error has been made, to correct such an error, draw a single straight line through the incorrect entry and enter the correct data above it. All such changes must be initialed and dated. DO NOT ERASE OR WHITE OUT ERRORS. For clarification of illegible or uncertain entries, print the clarification above the item, then initial and date it.

11 Study Monitoring, Auditing, and Inspecting

11.1 Study Monitoring Plan

It is the responsibility of the Principal Investigator to oversee the safety of the study at his/her site. This safety monitoring will include careful assessment and appropriate reporting of adverse events as noted above, as well as the construction and implementation of a site data and safety-monitoring plan. Medical monitoring will include a regular assessment, at least every 6 months, of the number and type of serious adverse events by an independent clinician, [name], Department of Medicine, Division of Hematology-Oncology. Additionally, the Medical Monitor will be consulted for protocol exceptions and deviations and as needed for decision-making regarding dose modifications, study eligibility, and any need to stop enrollment or the study for safety concerns.

This study will be monitored in accordance with the Cancer Center's Clinical Trials Scientific Review and Monitoring Committee (CTSRMC) Plan, approved by NCI during the Core Grant's most recent review. This plan requires that the investigator submit a study-specific plan outlining how data will be reviewed. In addition, the CTSRMC plan calls for an internal audit by the Cancer Center's Data Safety Committee twice yearly. The investigator will allocate adequate time for such monitoring activities. The Investigator will also ensure that the monitor or other compliance or quality assurance reviewer is given access to all the above

CONFIDENTIAL

This material is the property of the University of Pennsylvania.

noted study-related documents and study related facilities (e.g. pharmacy, diagnostic laboratory, etc.), and has adequate space to conduct the monitoring visit.

11.2 Auditing and Inspecting

The investigator will permit study-related monitoring, audits, and inspections by the IRB, government regulatory bodies, and University compliance and quality assurance groups of all study related documents (e.g. source documents, regulatory documents, data collection instruments, study data etc.). The investigator will ensure the capability for inspections of applicable study-related facilities (e.g. pharmacy, diagnostic laboratory, etc.).

Participation as an investigator in this study implies acceptance of potential inspection by government regulatory authorities and applicable University compliance and quality assurance offices.

12 Ethical Considerations

This study is to be conducted according to US and international standards of Good Clinical Practice (FDA Title 21 parts 50 and 56 and International Conference on Harmonization guidelines), applicable government regulations and Institutional research policies and procedures.

This protocol and any amendments will be submitted to a properly constituted independent IRB, in agreement with local legal prescriptions, for formal approval of the study conduct.

All subjects for this study will be provided a consent form describing this study and providing sufficient information for subjects to make an informed decision about their participation in this study. This consent form will be submitted with the protocol for review and approval by the IRB and CTSRMC for the study. The formal consent of a subject, using the IRB-approved consent form, must be obtained before that subject undergoes any study procedure. The consent form must be signed by the subject and the investigator-designated research professional obtaining the consent.

13 Study Finances

13.1 Funding Source

This clinical study, including correlative work, will be supported by funds provided by Eli Lilly Pharmaceuticals, Inc.

If condoms are used as a barrier method, a spermicidal agent should be added as a double barrier protection.

Cases of pregnancy that occur during maternal exposures to abemaciclib should be reported. If a patient is determined to be pregnant following abemaciclib initiation, she must discontinue treatment immediately. Data on fetal outcome and breast-feeding are to be collected for regulatory reporting and drug safety evaluation.

Abstinence at certain times of the cycle, such as during ovulation or after ovulation, or withdrawal are not acceptable methods. The list of methods above is not exhaustive and additional contraception methods may also be acceptable if approved by the study doctor.
